5.2.4. Sample Code

5.2.4.1 Stratified Log-Rank Test

```
proc lifetest data = TargDS method = KM conftype = linear;
  TIME TimeVAR * CensorVAR(1);
  STRATA StratifiedVARs / Group = TrtVAR;
  ods output HomTests = hom;
run;

/* Explanation of variables (the same applies hereinafter) */
/* TargDS: dataset to be analyzed */
/* TimeVAR: variable with the time to event or time to censoring */
/* CensorVAR: variable that provides event or censoring, in the sample above, 1 = censoring */
/* StratifiedVARs: variables handled as strata or subgroups such as allocation factors, more than one
variable is possible. */
/* TrtVAR: treatment arm [1: A(TAS-118/L-OHP), 0: B(S-1/CDDP)] */
```

5.2.4.2 Log-Rank Test

```
proc lifetest data = TargDS method = KM
  conftype = linear;
  TIME TimeVAR * CensorVAR(1);
  STRATA TrtVAR;
  ods output Quartiles = qua;
  ods output ProductLimitEstimates = est;
run;
```

5.2.4.3 Cox Proportional Hazards Model

```
proc phreg data = TargDS;
  class TrtVAR StratifiedVARs;
  model TimeVAR * CensorVAR(1) = TrtVAR StratifiedVARs
    / r1 TIES = BRESLOW;
  hazardratio TrtVAR / CL = Wald;
run;
```

5.2.4.4 Cox Proportional Hazards Model (by Baseline Characteristic Factor)

```
proc phreg data = TargDS;
  class TrtVAR StratifiedVAR;
  model TimeVAR * CensorVAR(1) = TrtVAR StratifiedVAR TrtVAR * StratifiedVAR
    / r1 TIES = BRESLOW;
  hazardratio TrtVAR / CL = Wald;
run;
```

```
/* More than one StratifiedVAR is prohibited. */
/* To create a forest plot in each Subgroup, use the following results: */
```

```
/* p-value of interaction: p-value of TrtVAR * StratifiedVAR */
/* HR and confidence interval in each Subgroup: HR of each category of StratifiedVAR */
```

5.2.4.5 Restricted Mean Survival Time (RMST)

The boundary time τ is assumed to be 36 months. For the calculation of the number of years, see Section 5.2.1.1.2.

For variance, standard output data from SAS will be used.

For the details of the calculation method, refer to “Measures to evaluate time-to-event responses—To understand restricted mean survival time (RMST),” which is provided by the Japan Pharmaceutical Manufacturers Association.¹¹⁾

```
/* Step1 If survival time is longer than 36 months, then change all subjects to censoring. */
data TargDS2;
  set TargDS;
  if TimeVAR > 36 then CensorVAR = 1;
run;

/* Step2 Calculate RMST */
proc lifetest data = TargDS2 conftype = linear timelim = 36;
  time TimeVAR * CensorVAR(1); /* Day * Censored or not (value at the time of censoring) */
  strata TrtVAR;
  ods output Means = pre_RMST /* Obtain RMST */
            ;
run;

/* Step3 Calculate the confidence interval in each arm and the difference in RMST and its 95%
confidence interval */
data rmst;
  set pre_RMST;
  CI_low = Mean - quantile('NORMAL', .975) * StdErr; /* Lower confidence limit */
  CI_up = Mean + quantile('NORMAL', .975) * StdErr; /* Upper confidence limit */
run;

/* Step 4 Calculate the between-group difference in RMST and its 95% confidence interval */
data rmstdiff;
  merge pre_RMST(where = (TrtVAR = "A(TAS-118/L-OHP)"))
        (keep = TrtVAR Mean StdErr
         rename = (Mean = Mean_A StdErr = StdErr_A))
        pre_RMST(where = (TrtVAR = "B(S-1/CDDP)"))
        (keep = TrtVAR Mean StdErr
         rename = (Mean = Mean_B StdErr = StdErr_B));
  diff = Mean_A - Mean_B; /* Difference in RMST */
  CIdiff_low = diff - quantile('NORMAL', .975) * sqrt(StdErr_A ** 2 + StdErr_B ** 2); /* Lower
confidence limit */
  CIdiff_up = diff + quantile('NORMAL', .975) * sqrt(StdErr_A ** 2 + StdErr_B ** 2); /* Upper
confidence limit */
run;
```

5.2.4.6 95% Confidence Interval of Between-Group Difference in MST by Bootstrap

Method

```
/* Step1 Run 2000 repetitions of sampling with replacement for the number of subjects to be analyzed in each arm. */
```

```
proc surveysselect data = TargDS method = urs rep = 2000
    rate = 1 seed = 20181122 out = out OUTHITS;
strata TRT01P;
run;
proc sort data = out;
    by Replicate;
run;
```

```
/* Step2 Calculate MST in each arm in each repetition */
```

```
proc lifetest data = out method = KM
    conftype = linear;
    TIME AVAL * CNSR(1);
    STRATA TRT01P;
    by Replicate;
    ods output Quartiles = qua;
run;
```

```
/* Step3 Calculate the between-group difference in MST in each repetition */
```

```
data MST;
    merge qua(where = (TRT01P = "A(TAS-118/L-OHP)" and Percent = 50) keep = Replicate
    TRT01P Percent Estimate rename = (Estimate = Estimate_A))
    qua(where = (TRT01P = "B(S-1/CDDP)" and Percent = 50) keep = Replicate TRT01P
    Percent Estimate rename = (Estimate = Estimate_B));
    by Replicate;
    mstdiff = Estimate_A - Estimate_B;
run;
```

```
proc sort data = MST;
    by mstdiff;
run;
```

```
/* Step4 Calculate the 2.5th percentile (lower confidence limit) and 97.5th percentile (upper confidence limit) */
```

```
proc univariate data = MST;
    var mstdiff;
    output out = MST_CI pctlpre = P pctlpts = 2.5 97.5;
run;
```

5.2.4.7 Stratified Cox Proportional Hazards Model

```
proc phreg data = TargDS;
    class TrtVAR StratifiedVARs;
    model TimeVAR * CensorVAR(1) = TrtVAR
        / r1 TIES = BRESLOW;
    strata StratifiedVARs;
```

```
hazardratio TrtVAR / CL = Wald;  
run;
```

5.2.4.8 Comparison of Proportions Between Treatment Arms

```
proc freq data = TargDS;  
  tables StratifiedVARs * TrtVAR / chisq fisher;  
run;
```

5.2.4.9 Confidence Interval of Proportion

```
proc freq data = TargDS;  
  tables KubunVAR / binomial;  
run;  
/* KubunVAR: variable that provides a category in which a proportion is calculated */
```

5.2.4.10 Wilcoxon Test (Two-Sample)

```
proc npar1way data = TargDS Wilcoxon;  
  class TrtVAR;  
  var StratifiedVAR;  
run;
```

Note: To avoid errors in ranking internally processed in SAS, the variance used in VAR statement will be rounded off to the ninth decimal place.

5.2.4.11 Confidence Interval of Median

```
proc univariate data = TargDS cipctldf;  
  var ady;  
run;  
/* Calculate a distribution-free confidence interval using the cipctldf option. */
```

5.2.4.12 Log-Rank Test Using Recalculated α

The log-rank test will be conducted according to the following procedures in this study:

- Using Proc Seqdesign, derive a boundary p-value for the primary evaluation at the time of sample size determination.
- Derive estimated maximum information to establish a boundary at the time of analysis.
- Based on the maximum information as derived above, use Proc Seqdesign to calculate a boundary at the time of each testing.
- In the second interim analysis, use Proc Lifetest to calculate rank-order statistics/covariance matrix in a log-rank test for actual accumulated data.
- Edit the results of Proc Lifetest for Proc Seqtest.
- Using Proc Seqtest, conduct a test based on the boundary calculated by Proc Seqdesign and the edited log-rank test statistics and calculate a boundary used in the analysis for the primary evaluation.
- In the analysis for the primary evaluation, use Proc Lifetest to calculate rank-order statistics/covariance matrix in a log-rank test for actual accumulated data.
- Edit the results of Proc Lifetest for Proc Seqtest.
- Using Proc Seqtest, conduct a test based on the boundary calculated by Proc Seqtest in the second interim analysis and the edited log-rank test statistics.

```
/* Derive a boundary p-value for the primary evaluation at the time of sample size determination. */
```

```

proc seqdesign altref=-0.287682072 errspend boundaryscale = pvalue;
/* The value of altref is the logarithmic value of 0.75, a hazard ratio of TAS-118/L-OHP to S-
1/CDDP as specified in the protocol. */

TwoSidedErrorSpending: design
method(alpha) = errfuncobf /* O'Brien-Fleming type alpha spending function */

info = cum(0.5, 1)
/* The value of info = cum is information fraction. */
/* The value is 0.5 when half of all events are accumulated, */
/* and the value of 1 when all events are accumulated. */

alpha = 0.05 /* Significance level */
nstages = 2 /* Number of tests */
alt = twosided /* Two-sided test */
stop = reject;
samplesize model = twosamplesurvival
(nullhazard = 0.047803254 acctime = 19 foltime = 19);
/* Into t in an exponential distribution  $S(t) = \exp(-\lambda t)$ , */
/* substitute an estimated MST of 14.5 in the S-1/CDDP arm as specified in the protocol to
calculate  $\lambda$ . */
/* Acctime and foltime are the accrual period and the follow-up period, respectively, as defined in
the protocol. */
ods output Boundary = boundpre;
run;

/* Derive estimated maximum information to establish a boundary at the time of analysis. */
data maxinfo;
set boundpre;
where _Stage_ = 2;
theta = log(0.75); /* Estimated logarithmic hazard ratio */
alpha = Bound_LA;
/* Estimated boundary p-value for the primary evaluation */
/* (Value derived by Proc Seqdesign: 0.0244997106 ) */

inva = quantile("normal",1-alpha);
beta =0.15; * power in the primary analysis;
invb = quantile("normal",1-beta);

maxinfo = ((inva + invb) / theta) ** 2; /* Estimated maximum information */
required = maxinfo * 4; /* For reference: required number of events */

call symput("maxinfo",strip(put(maxinfo,best)));
/* Convert the estimated maximum information used in Proc Seqdesign to a macro variable. */
run;

/* Calculate a boundary at the time of analysis using the converted maximum information. */
proc seqdesign altref=-0.287682072 errspend maxinfo = &maxinfo;
TwoSidedErrorSpending: design

```

```
method(alpha) = errfuncobf info = cum(0.5, 1) alpha = 0.05 nstages = 2
alt = twosided stop = reject;
samplesize model = twosamplesurvival
(nullhazard = 0.047803254 acctime = 19 folttime = 19);
ods output ErrSpend = ErrSpend;
ods output Boundary = bound_surv;
run;

/* Stratified log-rank test (the second interim analysis) */
/* MLIWN PSIWN CNTRYIWN means the allocation adjustment factors. */
/* Presence/absence of measurable lesion, ECOG PS, country */
/* TRT01P is an assigned treatment arm. */
proc lifetest data = ADTTE method = KM conftype = linear;
time AVAL * CNSR(1);
strata MLIWN PSIWN CNTRYIWN / Group = TRT01P;
ods output HomStats = outs;
ods output LogrankHomCov = outv;
run;

/* Edit the results of Proc Lifetest for Proc Seqtest. */
data logrank_result;
merge outs outv;
by TRT01P;
keep Variable _Scale_ _Stage_ StdErr Estimate;
Variable = 'Arm';
_Scale_ = "Score";
_Stage_ = 1; /* Designate which number is this test among the planned tests. */
/* Obtain a standard error from the element in the first row and the first column (= variance) of a
2 x 2 covariance matrix for the log-rank test. */
if _n_ = 1 then do;
StdErr = sqrt(A_TAS_118_L_OHP_);
Estimate = LogRank;
output;
end;
run;

/* Conduct a test using */
/* the boundary calculated by Proc Seqdesign and the edited log-rank test statistics. */
proc seqtest boundary = bound_surv boundaryscale = pvalue
parms(testvar = Arm) = logrank_result
errspendadj = errfuncobf /* O'Brien-Fleming type alpha spending function */
order = stagewise;
ods output test = test_surv1; /* Use as a boundary in the analysis for the primary evaluation. */
run;

/* Stratified log-rank test (analysis for the primary evaluation) */
proc lifetest data = ADTTE method = KM conftype = linear;
TIME AVAL * CNSR(1);
```

```

strata MLIWN PSIWN CNTRYIWN / Group = TRT01P;
ods output HomStats = outs2;
ods output LogrankHomCov = outv2;
run;

/* Edit the results of Proc Lifetest for Proc Seqtest. */
data logrank_result2;
  merge outs2 outv2;
  by TRT01P;
  keep Variable _Scale_ _Stage_ StdErr Estimate;
  Variable = 'Arm';
  _Scale_ = "Score";
  _Stage_ = 2; /* Designate which number is this test among the planned tests. */
  /* Obtain a standard error from the element in the first row and the first column (= variance) of a
2 × 2 covariance matrix for the log-rank test. */
  if _n_ = 1 then do;
    StdErr = sqrt(A_TAS_118_L_OHP_);
    Estimate = LogRank;
    output;
  end;
run;

/* Conduct a test using the boundary calculated in the second IDMC */
/* and the log-rank test statistics in the analysis for the primary evaluation. */
ods graphics on;
proc seqtest boundary = test_surv1  boundariescale=pvalue
  parms(testvar=Arm) = logrank_result2
  errspendadj = errfuncobf
  order = stagewise;
ods output test = test_surv2;
run;

```

5.2.4.13 Cochran–Mantel–Haenszel Test

```

proc freq data = TargDS;
  tables StratifiedVARs * TrtVAR * KubunVAR / cmh;
run;
/* KubunVAR: variable that provides a category in which a proportion is calculated */

```

5.2.5. Software to Be Used

The software to be used and the version are presented in Table 5-10.

Table 5-10 Software to be used and version

	Software and version
Operating system	Microsoft Windows 7
Statistical analysis software	SAS 9.4 or later

5.2.6. Dictionaries to Be Used

The dictionaries to be used in analyses are presented in Table 5-11.

Table 5-11 Dictionaries to be used

Term	Dictionary	Remarks
Adverse event term	MedDRA/J	
• System organ class will be coded by MedDRA System Organ Class (SOC) and symptoms by MedDRA Preferred Term (PT).• SOC will be sorted in the order of SOC codes, if presented.• PT will be sorted in the order of PT codes, if presented.• The latest version will be used whenever possible.
Concomitant medication name	WHO Drug Dictionary	
• Medications will be tabulated using Generic Medication Names.• Medications will be sorted in the order of Generic Medication Names.• The latest version will be used whenever possible.

6. Primary Endpoint Analyses

The details of the primary analysis and an overview of its sensitivity analyses and the secondary analyses of the primary endpoint are presented below.

6.1. Primary Analysis for Primary Objective

- The superiority of TAS-118/L-OHP to S-1/CDDP with respect to OS will be tested in the FAS population. As the test method, a stratified log-rank test will be conducted according to the following allocation adjustment factors: ECOG PS (0, 1), measurable lesion (1: yes, 0: no), and country (1: Japan, 0: Korea). If the data on ECOG PS and measurable lesion at randomization differ from the data entered in the CRF, the data obtained at randomization will be used.

6.2. Sensitivity Analyses of Primary Analysis

- In the FAS population, a stratified log-rank test will be conducted according to the allocation adjustment factors entered in the CRF.
- Using a log-rank test without any allocation adjustment factors, the analysis will be conducted.
- In the enrolled population, the primary analysis will be conducted.

6.3. Secondary Analyses of Primary Endpoint

- With the date of observed death as the event date and the date of the last survival confirmation as the censoring date, without consideration of the cutoff date, the same analysis as the primary analysis will be conducted.

The following secondary analyses of the primary endpoint will be conducted in the FAS population:

- The survival curve, MST, and 95% confidence interval will be estimated in each treatment arm. The between-group difference in MST and its 95% confidence interval (by the bootstrap method) will also be calculated. The RMSTs and their 95% confidence intervals will be estimated, with an RMST boundary of 3 years (36 months). In addition, the between-group difference in RMST and its 95% confidence interval will be calculated.
- The number of subjects at risk at 3-month intervals, cumulative event-free rate, and median follow-up period (time to censoring) and its 95% confidence interval will also be presented.
- Using a Cox proportional hazards model with the allocation adjustment factors of study treatment (1: TAS-118/L-OHP, 0: S-1/CDDP), ECOG PS (0, 1) at randomization, measurable lesion (1: yes, 0: no) at randomization, and country (1: Japan, 0: Korea) as covariates and a stratified Cox proportional hazards model according to the allocation adjustment factors, the hazard ratio for each covariate and its confidence interval will be estimated. To estimate the confidence interval of the hazard ratio corresponding to the primary analysis, the confidence level of the stratified Cox proportional hazards model is defined as follows: 100–significance level (%) used for the primary analysis. The 95% confidence interval will also be estimated.
- Using a Cox proportional hazards model with the allocation adjustment factors of study treatment (1: TAS-118/L-OHP, 0: S-1/CDDP), ECOG PS (0, 1) entered in the CRF, measurable lesion (1: yes, 0: no) entered in the CRF, and country (1: Japan, 0: Korea) as covariates and a stratified Cox proportional hazards model according to the allocation adjustment factors, the hazard ratio for each covariate and its 95% confidence interval will be estimated.
- Using a Cox proportional hazards model with study treatment (1: TAS-118/L-OHP, 0: S-1/CDDP) as a covariate, the hazard ratio for the covariate and its 95% confidence interval will also be estimated.
- For each allocation adjustment factor, the survival curve, MST, and 95% confidence interval will be estimated in each treatment arm. The between-group difference in MST and its 95% confidence interval (by the bootstrap method) will also be calculated. The RMSTs and their 95% confidence intervals will be estimated, with an RMST boundary of 3 years (36 months). In addition, the between-group difference in RMST and its 95% confidence interval will be calculated.
- The number of subjects at risk at 3-month intervals, cumulative event-free rate, and median follow-up period (time to censoring) and their 95% confidence intervals will also be presented. Among the allocation adjustment factors, ECOG PS and presence/absence of measurable lesion will be analyzed using both data obtained at randomization and data entered in the CRF.

- For each allocation adjustment factor, using a Cox proportional hazards model with study treatment alone as a covariate and a Cox proportional hazards model with the allocation adjustment factors that have not been used for subgrouping and study treatment as covariates, the hazard ratio between study treatments and its 95% confidence interval will be estimated. Furthermore, the distribution of survival time will be compared between the treatment arms by a log-rank test and a stratified log-rank test according to the allocation adjustment factors that have not been used for subgrouping. Among the allocation adjustment factors, ECOG PS and presence/absence of measurable lesion will be analyzed using both data obtained at randomization and data entered in the CRF.
- For each baseline characteristic factor listed in Table 5-7 in Section “5.2.2 Patient Baseline Characteristics” and each allocation adjustment factor, the MST and its 95% confidence interval will be presented in each treatment arm, and the hazard ratio and its 95% confidence interval will be estimated by a Cox proportional hazards model. The covariate of the model will be study treatment only. The confidence interval of the hazard ratio between the treatment arms will be illustrated in a forest plot, and the p-value of interaction between treatment response and each baseline characteristic factor will be presented to check the uniformity among the strata. The following three covariates will be used to calculate the p-value of interaction in the Cox proportional hazards model: study treatment, baseline characteristic factor, and interaction between study treatment and baseline characteristic factors.
- A breakdown of events and censoring will be tabulated in each treatment arm, and the same analysis will also be conducted by country.
- If the assigned treatment differs from the actual treatment given to a subject, a stratified log-rank test will also be conducted by handling the actual treatment given to the subject as the treatment arm.

7. Secondary Endpoint Analysis

An overview of the main analyses of the secondary endpoints is presented below.

To compare with data from literatures, a confidence coefficient of 95% will be used to present the confidence interval.

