16.3.2 Primary Endpoint Analyses

Main methods of primary endpoint (OS) analysis are shown below.

(1) Primary analysis

- OS in the FAS will be compared between the two study treatment arms using stratified log-rank test by three stratification factors (significance level is 5% for 2 sided test). 0.305% and 4.899% are set at the time of second interim and main evaluation respectively by alpha spending function with O'Brien-Fleming form and considering correlation between each test statistic to maintain significance level throughout the study less than or equal to 5%. Superiority of efficacy of TAS-118/L-OHP arm to S-1/CDDP arm is statistically considered valid when either p-values are less than or equal to each significance level in each statistical test. Also, a confirmation of the superiority in the first interim analysis will not be done.

(2) Sensitivity analyses of primary analysis

- OS in the FAS will be compared between the two study treatment arms using unstratified log-rank test. In addition, Cox Proportional Hazard (CPH) model will be performed with the study drug as covariate.

(3) Secondary analysis of primary endpoint

Following analyses will be performed in FAS population.

- Hazard ratio of OS with 95% confidence interval will be estimated by CPH model with the study drug and three stratification factors as covariates.
- In each study treatment, survival curves of OS will be estimated and Median Survival Time (MST) with 95% confidence interval using the Kaplan-Meier method will be presented. Otherwise the number at risk and cumulative event free rate every three months will be presented.

- In each stratification factor and each study treatment, survival curves of OS will be estimated and MST with 95% confidence interval using the Kaplan-Meier method will be presented. Otherwise the number at risk and cumulative event free rate every three months will be presented.

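### The OS subgroup and interaction Cox models leave out the randomisation factors, which pulls subgroup hazard ratios toward 1 and costs the interaction test some power

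*SAP*

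**What the plan says.** For each Table 5-7 factor and each allocation factor, SAP 6.3 plans an OS hazard ratio by category, a forest plot and an interaction p-value, all in the FAS.

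- Hazard ratio by category: "The covariate of the model will be study treatment only".
- Interaction p-value, three terms: "study treatment, baseline characteristic factor, and interaction between study treatment and baseline characteristic factors".
- The code in SAP 5.2.4.4 fits treatment, one factor and their product. A comment rules out further terms: "More than one StratifiedVAR is prohibited". Another says where the forest-plot figures come from: "HR and confidence interval in each Subgroup: HR of each category of StratifiedVAR".

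Elsewhere the allocation factors are used. For the primary test in SAP 6.1, "a stratified log-rank test will be conducted according to the following allocation adjustment factors": ECOG PS, measurable lesion and country. For the overall OS hazard ratio, SAP 6.3 plans a covariate-adjusted, a stratified and a treatment-only Cox model. For subgroups defined by an allocation factor it plans, beside a treatment-only model, "a Cox proportional hazards model with the allocation adjustment factors that have not been used for subgrouping and study treatment as covariates", and log-rank tests stratified by the remaining factors. That part contains no interaction test.

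**The concern.** For Table 5-7 factors that are not allocation factors (sex, age, histology, prior gastrectomy, metastatic sites and others), the SAP writes down no adjusted subgroup hazard ratio. For no factor at all does it write down an interaction test adjusted for the other allocation factors.

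The plan itself gives reason to expect the omitted factors to matter. Protocol 26.1 chose PS because of its large effect on prognosis and measurable-lesion status because it may have one. SAP 5.2.2 counts PS in its JCOG risk index. The case for country is weaker.

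Leaving a prognostic covariate out of a Cox model moves the treatment hazard ratio toward 1, and an interaction term shrinks in the same way. At stake is how well the forest plot and the interaction p-values, which the SAP offers as its check of uniformity across strata, can show real heterogeneity.

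**Working it through.** **1. The plan's own figure.** The protocol sets the nominal levels: "0.305% and 4.899% are set at the time of second interim and main evaluation respectively". Schoenfeld's formula with hazard ratio 0.75, 85% power and 1:1 allocation gives (1.9687 + 1.0364)² / (0.25 × 0.2877²) = 9.031 / 0.02069 = 436.5, so 437 deaths, as stated in Protocol 16.4 and SAP 2.1.2. All 49 cells of the power table also reproduce. At the revised 491 deaths, power is Φ(0.2877 × √(491/4) − 1.9687) = Φ(1.219) = 88.9%. The point here touches none of this. The documents state no power for the interaction tests.

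**2. What the interaction test can do at 491 deaths.** With a share p of deaths in one category, SE = √(4/(Dp) + 4/(D(1−p))). For D = 491 and p = 0.5 this is √(8/245.5) = 0.181. At two-sided 5%:

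- ratio of hazard ratios 0.75: Φ(0.2877/0.181 − 1.96), about 36% power;
- ratio 0.60: Φ(0.5108/0.181 − 1.96), about 81%;
- ratio detectable with 80% power: exp(−2.80 × 0.181) = 0.60.

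**3. Effect of the omitted factors.** Simulation with 2,000 trials per scenario, 650 patients (FAS target), 491 deaths and minimisation on three binary factors. Assumed, not in the documents: factor prevalences 45%, 75% and 50%; the same prognostic hazard ratio for each factor; a subgroup factor independent of the three; a true ratio of hazard ratios of 0.6. The Monte Carlo standard error on power is about 1 point.

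| Prognostic HR per factor | Interaction power, 50/50 split: as planned / adjusted | 20/80 split: as planned / adjusted | Mean subgroup HR when the truth is 0.75 (50/50 split): as planned / adjusted |
|---|---|---|---|
| 1.0 | 79.2% / 78.5% | 55.4% / 55.4% | 0.754 / 0.753 |
| 1.3 | 77.8% / 79.7% | 54.6% / 55.5% | 0.759 / 0.753 |
| 1.6 | 73.4% / 79.4% | 50.2% / 54.9% | 0.770 / 0.753 |
| 2.0 | 67.3% / 79.7% | 45.4% / 55.2% | 0.785 / 0.754 |

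The power differences are 1.9 and 0.9 points at 1.3, 6.0 and 4.7 at 1.6, and 12.4 and 9.8 at 2.0. With no true interaction, the rejection rate is 4.4% to 6.0% under either model.

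**4. Cross-check under other assumptions.** A smaller simulation (700 to 800 trials per setting) used prevalences of 45%, 80% and 60%, and treatment hazard ratios of 0.9 and 0.6 in two equal subgroups. With prognostic hazard ratios for PS, measurable lesion and country of 1.3/1.2/1.2, 1.5/1.3/1.3 and 2.0/1.5/1.5, adjustment raised interaction power from 60.3% to 62.1%, 56.9% to 60.3% and 48.0% to 58.9%. Direction and rough size agree.

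**5. Variability.** At a prognostic hazard ratio of 1.6 and a 50/50 split, the SD of the subgroup log hazard ratio is 0.126 unadjusted and 0.132 adjusted. In a category of about 65 patients, in the smaller simulation, it is about 0.30 and 0.33. Within one trial the two log estimates differ with an SD of 0.03 to 0.06 (50/50 split) or 0.06 to 0.12 (20% subgroup) over prognostic hazard ratios 1.3 to 2.0.

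**6. Text against code.** SAP 6.3 takes the subgroup hazard ratio from a treatment-only model by category, so each category has its own baseline hazard. The comments in 5.2.4.4 take it from the interaction model, where the categories share one baseline hazard up to a constant. The two need not give the same numbers.

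**The case against.** The strongest reply is that a treatment-only forest plot is a legitimate and transparent choice for secondary analyses that carry no alpha. Protocol 16.3.2 asks for no subgroup hazard ratios or interaction tests beyond Kaplan-Meier summaries by stratification factor. Marginal and conditional hazard ratios are different targets, and the SAP sets no conditional target for subgroups. Event count limits the interaction test more than this omission does. SAP section 9 also says that the full list of analyses is in a separate output plan, which is not available here, so an adjusted version may exist. All of this stands and keeps the point small.

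Three stronger readings are tempting, and the documents do not support them:

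- A reader might infer that the interaction model is also treatment only. It is not; the SAP lists three terms for it.
- A reader might infer that chance imbalance makes the unadjusted subgroup estimates unreliable. Imbalance can shift an individual estimate, but the unadjusted log hazard ratio is no more variable than the adjusted one. The gap between the two in a given trial does not show which is wrong.
- A reader might infer that the overall and subgroup estimates in one plot come from different models. SAP 6.3 does not say which overall estimate the plot shows, if any, and it also plans a treatment-only overall hazard ratio.

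Nor is the interaction model the only look at consistency. For PS, measurable lesion and country, SAP 6.3 already gives adjusted hazard ratios and stratified tests by subgroup.

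**Conclusion.** The point holds as a minor one. Adjusted subgroup hazard ratios are missing from the SAP for Table 5-7 factors other than the allocation factors, and interaction tests adjusted for the remaining allocation factors are missing for all. The cost is attenuation toward 1 and a loss of interaction power that runs from nothing when the factors are not prognostic to about 10 to 12 points when all three have a prognostic hazard ratio of 2.0. The size rests on assumed prognostic strengths, prevalences and a true ratio of 0.6. Adjustment does not rescue a test with about 36% power for a ratio of 0.75. Type I error, the primary test and its matching hazard ratio are unaffected. The mismatch between the SAP 6.3 text and the code comments in 5.2.4.4 does not depend on any of these assumptions.

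**What to change.** - In the Table 5-7 bullet of SAP 6.3 and the code in 5.2.4.4, add the allocation factors at randomisation that do not define the subgroup as main-effect covariates, both to the subgroup hazard-ratio models and to the interaction model. This extends what SAP 6.3 already does for allocation-factor subgroups.
- Report the adjusted hazard ratios and interaction p-values beside the treatment-only results.
- In categories too small to support the extra covariates, show the treatment-only result alone. Some Table 5-8 categories are likely to be sparse or empty: brain metastasis is an exclusion criterion, and known HER2-positive patients are not eligible.
- For PFS, use the CRF-entered factors, as SAP 7.1.2 requires. SAP 7.1.3 sets the same rule for TTF.
- In the same edit, state which model supplies the forest-plot hazard ratios, so that SAP 6.3 and the comments in 5.2.4.4 agree.

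The cost is SAP wording and small code changes on data already collected; SAP section 8 provides the revision route. The statistical price is a slightly more variable estimate in small categories (SD of the log hazard ratio about 0.33 against 0.30 at about 65 patients).
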